### 3.3 Secondary Study Endpoints

To conduct an exploratory analysis of the effect of this intervention on healthcare utilization and engagement, drinking outcomes, and quality of life. We will also explore patient-level predictors of effectiveness.

We will explore the relative efficacy of XR-NTX+CM to standard care on decreasing acute healthcare use (ED, inpatient, Emergency Medical Services), associated expenditures, and cost-effectiveness. Secondarily, we will explore effects on healthcare engagement (clinic use, medication adherence, motivation to change), alcohol quantity/frequency, alcohol-related problems, and quality of life measures.

CONFIDENTIAL

This material is the property of the NYU School of Medicine and Langone Medical Center. Do not disclose or use except as authorized in writing by the study sponsor

See Attachment #2. We will evaluate and compare the performance of CDT and the combination of CDT-GGT as an objective measure of alcohol consumption and its correlation to self-report. We will also conduct an exploratory analysis of patient and system characteristics possibly associated with effectiveness. These data will be used to inform the individualization of treatment choice to maximize the probability of successful outcome. Factors assessed will include data collected in ongoing investigations of pharmacotherapy for alcohol dependence to facilitate comparison across study populations and settings. This specifically includes the analyses modeled on those performed in an ongoing study directed by [name] (R01AA020836; S12-02263) at NYU. All data analyzed will be de-identified and linked by a unique identification number.

### **3.4 Primary Safety Endpoints**

XR-NTX is already FDA approved for the indication of alcohol dependence for which it will be used in this study. We will repeat laboratory analyses (liver enzymes (AST, ALT, GGT), pregnancy, urine drug screen) as specified and maintain an adverse-effect profile and drug accountability log. Clinical assessments completed at week 1 and at Medical Management-Injection visits will include progress notes and Adverse Event Forms. We will use vital statistics to track mortality in the event of drop-out.

## **4 Subject Selection and Withdrawal**

### **4.1 Inclusion Criteria**

Subjects must meet all of the following criteria to be eligible for study enrollment:

- 1) English or Spanish speaking\*  
\*Non-English Spanish speaking patients will not be enrolled initially until study documents have been translated, back translated, and approved by the IRB. This will be done through a subsequent amendment.
- 2) Emergency Department patient
- 3) Aged 18-80
- 4) Have had 6 or more emergency department visits in the last 24 months, with at least 3 visits in the last 12 months. Period of time can be extended by up to 6 months if incarcerated or institutionalized for  $\geq$  6 months.
- 5) Meet DSM-IV criteria for alcohol dependence or & DSM-V criteria for alcohol use disorder, moderate or severe.
- 6) Have  $\geq$ 2 days/week of heavy drinking ( $>4$  drinks/day)
- 7) Capable of giving informed consent.

### **4.2 Exclusion Criteria**

Subjects who meet any of the following criteria will be ineligible for study enrollment:

- 1) Current physiologic dependence to opioids
- 2) Acute or chronic pain requiring opioid treatment
- 3) Acute liver injury (liver aminotransferase concentrations  $>5$  times the upper limit of normal)
- 4) Health condition considered unsafe for inclusion (at discretion of PI and/or attending physician)
- 5) Lack of capacity or willingness to consent
- 6) Currently prescribed pharmacotherapy for alcohol dependence (not including treatment of acute alcohol withdrawal syndrome)
- 7) Currently enrolled in research in which the intervention includes treatment for alcohol or substance use disorders, pharmacotherapy, or that may otherwise interfere with the study or patient safety.
- 8) Previous significant adverse reaction to naltrexone or diluent
- 9) Pregnant, nursing, or not using effective methods of birth control
- 10) Prisoners (as defined by Office of Human Research Protection) at the time of enrollment ARE NOT ELIGIBLE for study entry.
  - However, subjects who become prisoners after being enrolled will be included and not be withdrawn from the study

CONFIDENTIAL

This material is the property of the NYU School of Medicine and Langone Medical Center. Do not disclose or use except as authorized in writing by the study sponsor

- Patients on parole or probation are eligible for enrollment.

### **4.3 Subject Recruitment and Screening**

All research will be performed on the NYU School of Medicine campus and Bellevue Hospital Center by study investigators. Recruitment will take place in the Bellevue ED (inclusive of Department of Emergency Medicine clinical and nonclinical space to ensure privacy and to minimize disruption of ongoing ED care). Follow up visits will occur in the Bellevue ED, Bellevue ambulatory care clinic, or the Clinical and Translational Science Institute Clinical Research Center. If it is only possible for subjects to conduct research assessments off site (e.g. due to mobility, health, or legal reasons), investigators may follow up with subjects off site.

#### **4.3.1 Prescreen:**

Potentially eligible patients will be identified in part through an administrative database search of Bellevue Hospital billing records. The data received includes a list of patients (name, date of birth, medical record number, number of visits) who had 6 or more ED visits within a 24-month period, with at least 3 visits in the past 12 months, and who were assigned an alcohol-related diagnosis; we will receive two years of data at a given time. Patients who have met this threshold are considered high-risk and added to an automated alert system to facilitate potential intervention. This alert system was first developed as part of a Medicaid High Cost Care Initiative demonstration project (PI: [name], R# 06-336 and 06-412). It remains in use for various quality improvement initiatives, including for the population being studied—frequent ED users with alcohol dependence. [name] remains involved in the process of identifying high-risk patients with substance abuse diagnoses via his role as a member of Bellevue Hospital care management committees.

The high-risk patients added to the alert system are “Prescreened” as potentially eligible for study inclusion because, by definition, all will meet the visit threshold and were previously assigned an alcohol-related diagnostic code. They will be added to the briefly, aforementioned alert system. Upon registration of potentially eligible patients in the ED, an automated alert will be delivered by secure email to the ED social worker, care manager, and the study PI ([name]). This alert triggers consultation by the social worker or care manager (as part of the quality improvement initiative) and alerts [name] of a potential candidate for study inclusion. This system also ensures patients are identified promptly to facilitate for enrollment and for follow-up assessments.

ED staff/providers (inclusive of ED physicians, nurse practitioners, nurses, social workers, health coaches, and care managers) also may notify study investigators (PI/RA) of potentially eligible ED patients, who may not have been identified through the alert system (e.g. due to miscoded diagnoses, outdated patient lists, and/or the alert system being unavailable for maintenance, etc.). These patients may be added to the alert system (if appropriate). Staff referrals to the study do not necessarily need to originate from the alert system, as long as eligibility criteria are met. Research staff will remind ED clinical staff about the study and its eligibility criteria to help ensure appropriate referrals.

#### **4.3.2 Screen (in Bellevue ED):**

Recruitment will be triggered primarily by the aforementioned alert system or ED staff referral. Screening will be performed via convenience sample, dependent on the availability of the study investigators (PI/RA). Recruitment during days, nights, and weekends will be scheduled to capture a representative sample. A limited number of patients may be held overnight in ED observation, providing additional opportunities for enrollment. We may oversample women and minorities to reach enrollment targets.

Prior to approaching a patient for potential enrollment, the PI/RA will speak with ED staff/provider caring for the patient to ensure that the patient is appropriate and willing to be approached. The provider will introduce the PI/RA to clinically sober and medically stable patients who have given their permission to be approached. The PI/RA will describe the study to the patient.

CONFIDENTIAL

This material is the property of the NYU School of Medicine and Langone Medical Center. Do not disclose or use except as authorized in writing by the study sponsor

### 4.3.3 Capacity Assessment, Informed Consent, and Enrollment

The PI and RA will obtain subjects' written informed consent only after assessing their capacity to consent using the following stringent procedures. The recruitment process will specifically address the likelihood that the subjects may have a compromised capacity to consent. Subjects will not be enrolled until clinically sober and medically stable. Subjects may be (re)assessed multiple times during their ED visit(s) as needed—and therefore will have multiple opportunities to be enrolled. We will use techniques shown to improve comprehension in informed consent procedures such as using a lower reading level, using larger typeface, quizzing and having multiple individuals providing the information. The PI will provide sensitivity training of investigators/RAs regarding difficult behaviors and limited comprehension and assessment of subject capacity to consent.

The PI/RA will assess subject's understanding of the study and capacity to consent to it using the **University of California San Diego Brief Assessment of Capacity to Consent to Research (UBACC)** (Attachment #2). The UBACC 10-item questionnaire is a 5-minute, easy-to-use, and validated tool, which we have studied in this population. It rates the basic elements of capacity (understanding, appreciation, reasoning, and ability to express a choice) to identify subjects with questionable capacity to consent to a specified research project. The UBACC assessment occurs after informing potential subjects about the study. Thus, first the RA/PI will review each page of the informed consent document with the patient, pausing to reassess comprehension throughout the process. Then, the RA/PI will administer the UBACC. Once the RA/PI confirms the subject's comprehension (with the UBACC), the RA/PI will request the patient's signature and provide the patient with a copy of the signed consent document. If, at any point during the consent process, the RA/PI does not believe the subject comprehends the study procedures the patient will not be enrolled at that time, but he or she may be eligible in the future. Patients who are not able to successfully complete ("pass") the UBACC may be further assessed by psychiatry consultation.

In addition, the PI/RA will ask the subject to consent to being audio recorded (for qualitative interviews, counseling sessions, and quality assurance monitoring). If the patient declines to provide their written informed consent to be recorded, the subject may still participate in the study (i.e. audio recording is optional).

Subjects may be required to sign separate authorization forms for release of their personal health information to and from entities involved in their care, including care managers, case workers, housing facilitators, health providers, and government agencies/institutions. These data will be used to help coordinate and facilitate health and social needs and track outcomes. The purpose of this will be primarily clinical, rather than research. Each institution will ensure protection of PHI. All institutions, with the exception of the NYC Department of Homeless Services, are HIPAA covered entities. All Institutions will consult their respective IRBs; the NYC Fire Department Emergency Medical Services will use the IRB of the NYC Department of Health and Mental Hygiene.

### 4.3.4 Additional Post-Consent Eligibility Assessment

After obtaining informed consent, we will confirm eligibility by performing a chart and laboratory review (liver enzymes, pregnancy, urine drug screen), history and examination, diagnostic interview to confirm alcohol dependence, and assessment of opioid use and chronic pain. See also Sections 4.1 and 4.2 for Inclusion and Exclusion Criteria.

### 4.3.5 Subject Randomization

Subjects will be randomly assigned to one of two arms: Intervention or Standard Care. The randomization will be completed using a random number generator with randomly permuted blocks in blocks of 2, 4, and 6 subjects. Randomization is embedded and performed within the secure REDCap software electronically. After subjects have provided their informed consent to participate in the study, are determined to be eligible for it, and have completed all baseline assessments, the RA or PI will click on the randomization button in REDCap for the treatment assignment.

CONFIDENTIAL

This material is the property of the NYU School of Medicine and Langone Medical Center. Do not disclose or use except as authorized in writing by the study sponsor

#### **4.3.6 Expected Human Subjects Characteristics**

Based on preliminary studies, this population will have a mean age  $50 \pm 10$ , and be predominantly male, ethnically diverse, be without other usual source of care, and be precariously housed or homeless. Approximately forty-five percent of Bellevue patients are of Hispanic/Latino ethnicity (representing many countries), 40% are African American (including Caribbean and African immigrants), 10% are Asian American. Overwhelmingly, the major payers are Medicaid, Bad Debt and Charity Pools from state and federal programs. Based on studies of this population, including our own, comorbidities are expected to include concurrent mental illness, nicotine and other substance use, and untreated chronic conditions, often related to chronic alcohol dependence. In a recent dataset of 129 individuals with frequent Bellevue ED use an assigned alcohol-related diagnosis, 124 were male and 5 were female. This marked disparity among frequent ED users with AUDs has been consistently observed at Bellevue and internationally. There will be no special outreach programs to recruit females or minorities since subjects will be drawn from patients receiving care at the Bellevue Hospital Emergency Department and must meet study inclusion criteria. We will purposefully recruit females by using a lower threshold of baseline visits for their addition to the alert system used in the recruitment procedure (but all subjects will meet inclusion criteria as defined). This same procedure will be performed, as needed to ensure ethnic diversity that is representative of the overall Bellevue population.

Prisoners (at the time of enrollment), pregnant females, persons under the age of 18 or over the age of 80, and persons who lack decisional capacity, or do not consent to the study will not be included. Additional exclusionary criteria exist for those recruited for the clinical intervention trial, including active opioid dependence, acute or chronic pain requiring opioid treatment, acute liver injury/failure (liver aminotransferase concentrations  $>5$  times the upper limit of normal), any medical condition considered by the PI to be incompatible with or unsafe for study inclusion (e.g. expectation of future opioid needs), previous significant adverse reaction to naltrexone, body habitus that precludes safe injection, or individuals currently being prescribed outpatient addiction pharmacotherapy. If a woman becomes pregnant during the study she will be removed from the study and appropriately referred. We have chosen to include an age range to 18 to 80 to reduce confounding influences. To our knowledge, XR-NTX has not been studied in persons over the age of 80 or under the age of 18; persons of this age will not be included in this pilot study. All Federal rules regarding vulnerable subjects will be incorporated into the study protocol, and reviewed by the NYU IRB.

### **4.4 Early Withdrawal of Subjects**

#### **4.4.1 When and How to Withdraw Subjects**

- Subjects will be withdrawn from the study who: withdraw consent, become pregnant, develop a health condition in which XR-NTX is contraindicated (including need for opioid pain control). Abrupt termination of study treatment should not affect subject safety beyond its disease mitigating effects on alcohol dependence. Appropriate referral will be made for ongoing and/or alternative addictions treatment for all subjects withdrawn from the study.
- Subjects who are not adherent to the research protocol treatment schedule will not be withdrawn. XR-NTX administration will be allowed to resume after missed visits/injections, which is expected in this patient population due to subject-level factors such as psychosocial challenges, potential incarceration or transient medical conditions that may prevent or delay safe injection (e.g. elevation in aminotransferase elevation  $>5$  times the upper limit of normal). The window for subjects to receive XR-NTX injections will not close until the 12th month after subject enrollment. Contraindications to treatment re-initiation (opioid dependence) will be reassessed.
- To help minimize attrition and departure from protocol, we will provide incentives for subject visits, use previously piloted care coordination and subject tracking measures, and allow considerable flexibility through the pragmatic design of the study.

CONFIDENTIAL

This material is the property of the NYU School of Medicine and Langone Medical Center. Do not disclose or use except as authorized in writing by the study sponsor

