Protection against Risk (XR-NTX): As per exclusion criteria, the PI will avoid administering XR-NTX in patients with medical conditions that would contraindicate its use. Specifically, XR-NTX will not be used in: active opioid dependence (including any individual whose urine drug screen is positive for opioids), acute or chronic pain requiring opioid treatment, acute liver injury/failure (liver aminotransferase concentrations  $>5$  times the upper limit of normal), any medical condition considered by the PI to be incompatible with or unsafe for study inclusion (e.g. expectation of future opioid needs), lack of decisional capacity, refusal to consent, currently being prescribed outpatient addiction pharmacotherapy (other than treatment of alcohol withdrawal), previous significant adverse reaction to naltrexone, poly(lactide-co-glycolide, carboxymethylcellulose, or any other components of the diluent, body habitus that precludes safe injection, children, or pregnancy. The PI will assess liver function prior to enrollment; persons with liver aminotransferase concentrations  $>5$  times the upper limit of normal will not be eligible for enrollment. Subjects will be monitored for signs and symptoms of liver injury at subsequent XR-NTX administration visits and research visits. Subjects in both arms will have their liver enzymes tested at enrollment and at the 3-, 6-, and 12-month research visits. The PI will repeat liver enzyme testing if subject receiving XR-NTX through the study has signs or symptoms of liver injury. If the liver aminotransferase concentrations rise to  $>5$  times the upper limit of normal, the laboratory tests will be repeated in one week. If liver enzymes are persistently elevated or if the individual is symptomatic, study medication will be discontinued and the subject will be referred for a Hepatology evaluation.

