In case of an emergency situation requiring opioids, subjects will be provided with a card showing that they have (or have not) received XR-NTX. This card will provide detailed information to medical personnel describing the special precautions necessary in the event that the subject should require pain management. Specifically, the amount of opioids necessary for analgesia may be greater than usual, and the resulting respiratory depression may be deeper and more prolonged. As a result, a rapidly acting analgesic that minimizes respiratory depression is preferred and the amount of the analgesic administration titrated to the needs of the patient in a setting equipped and staffed for cardiopulmonary resuscitation. The name of and contact information for the study PI and phone number of will be listed on the card in the event of an emergency. Unexpected visits related to side effects and adverse events will be accommodated (in the ED or clinic), and the PI will be available by phone for emergency consultation at any time.

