## 5.6 Prior and Concomitant Therapy

As per eligibility criteria, patients actively being treated with pharmacotherapy for opioid or alcohol dependence (not including treatment of alcohol withdrawal syndrome) will not be eligible for study inclusion. Otherwise, subjects may receive any concomitant medical therapy.

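### Sections 4.4.1 and 4.3.6 take subjects out of the study, in either arm, for pregnancy or an XR-NTX contraindication, and no rule keeps their follow-up data for the all-randomized analysis

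*Combined protocol and SAP*

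**What the plan says.** **The withdrawal rule.** Section 4.4.1: "Subjects will be withdrawn from the study who: withdraw consent, become pregnant, develop a health condition in which XR-NTX is contraindicated". The same sentence counts a need for opioid pain relief as such a condition. Section 4.3.6 adds: "If a woman becomes pregnant during the study she will be removed from the study and appropriately referred". Neither text is confined to subjects assigned to XR-NTX. The second bullet of 4.4.1 exempts missed treatment and temporary conditions, including a passing aminotransferase rise.

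**The data rules.** Section 4.4.2 covers two groups. Subjects who withdraw consent are asked to allow survival data and, beyond that, the complete data set. Subjects lost to follow-up have mortality tracked through vital statistics. Sections 3.4 and 7.2.2 (Safety Monitoring) add mortality tracking after drop-out. Nothing addresses a subject whom the investigator withdraws and who has not withdrawn consent.

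**The liver rule.** Section 1.6.1, for enzymes that stay raised or are accompanied by symptoms: "study medication will be discontinued and the subject will be referred for a Hepatology evaluation". It does not mention leaving the study.

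**The analysis.** Section 7.3 takes every randomized subject, treated or not, for primary and secondary aims. Section 7.2.2 (Aim 2) plans an intention-to-treat analysis of healthcare use and expenditures.

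**The concern.** An all-randomized analysis needs outcomes from all randomized subjects. A rule that removes people after randomization because of the suitability of one arm's drug cuts into that, and for standard-care subjects, who receive no XR-NTX from the study, it serves no treatment purpose.

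The data rules also produce an odd ordering. Someone who revokes consent is asked for the full data set, while someone who still consents but is removed by rule falls under no data rule.

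The outcomes exposed are those gathered at research visits: TLFB drinking, EQ-5D, SIP-2R, craving and CDT. If removal differs by arm, and those removed differ from those who stay, the comparison can be biased in either direction. Detection could differ by arm. Sections 6.3 to 6.13 schedule intervention visits every 4 weeks with adverse-event review, pregnancy testing where relevant and symptom-driven liver tests. After week 1, standard care has only the three research visits (Section 6.2).

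**Working it through.** **1. Passages side by side**

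| Event | Section | Stated consequence | Data afterwards |
|---|---|---|---|
| Lasting contraindication, including opioid need | 4.4.1 | leaves study | no rule |
| Pregnancy | 4.3.6, 4.4.1 | leaves study | no rule |
| Persistent or symptomatic enzyme elevation | 1.6.1 | medication stopped, referral | participation not mentioned |
| Missed treatment, temporary condition | 4.4.1 | not withdrawn | continues |
| Consent withdrawn | 4.4.1, 4.4.2 | leaves study | permission sought, up to full data |
| Lost to follow-up | 4.4.2 | none stated | mortality |

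The first two rows conflict with Section 7.3. The third row must be reconciled with the first.

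**2. The plan's own sample size (Section 7.1)**

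Inputs: 6-visit difference, SD 15, alpha 0.05 (taken as two-sided; the plan does not say). The standardized effect is 6/15 = 0.40. A two-sample t-test needs 99.1 per arm at 80% power and 132.3 at 90%, which round up to the plan's 100 and 133. At 125 per arm the detectable effect at 80% power is 0.356 SD, consistent with the plan's value of slightly under 0.40.

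**3. Power if outcomes are lost equally in both arms (assumed rates)**

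Normal approximation, effect 0.40 SD, n = 125 × (1 − loss):

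- no loss, n = 125: 88.5%
- 5% loss, n = 118.75: 86.9%
- 10% loss, n = 112.5: 85.1%
- 20% loss, n = 100: 80.7%

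Power is not the main issue.

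**4. Bias in research-visit outcomes, phase 2 (assumed rates)**

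Let w_i and w_c be the fractions removed in the intervention and control arms. Let δ be how far the mean of those removed lies from the mean of those remaining, in SD, equal in both arms. Using only those remaining misstates each arm's mean by w × δ, so the arm difference is off by (w_i − w_c) × δ. A positive value means the intervention looks better if those removed do worse.

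| Removed, intervention vs control | δ = 0.5 | δ = 1 |
|---|---|---|
| 10% vs 2% | 0.08 × 0.5 = 0.04 | 0.08 × 1 = 0.08 |
| 4% vs 2% | 0.02 × 0.5 = 0.01 | 0.02 × 1 = 0.02 |
| 2% vs 6% | −0.04 × 0.5 = −0.02 | −0.04 × 1 = −0.04 |
| equal | 0 | 0 |

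The largest entry is 0.08/0.356 = 22% of the detectable effect. If δ differs between arms, equal removal no longer gives exactly zero.

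**5. Feasibility proportions, phase 1**

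Fifty subjects in two arms is about 25 per arm. One rule-based withdrawal counted as a non-completer lowers assessment completion by 1/25 = 4 points in that arm and 1/50 = 2 points overall. Any non-completer has this effect. The difficulty is that the Aim 1 proportion does not separate removal by rule from failure to engage.

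**The case against.** The best counter-reading is that the sponsor meant only to stop the drug. After the withdrawal sentence, 4.4.1 turns to abrupt ending of study treatment, and its next bullet discusses restarting treatment. Section 3.1 schedules the research visits for both arms without exception. This shows that a literal data stop is an inference, and that much stands. It does not settle the matter: the first bullet speaks of leaving the study at both its start and its end, and the second exempts only non-adherence and temporary conditions.

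Several safeguards also stand. Sections 7.2.1 and 7.2.2 draw healthcare use from hospital, ambulance and Medicaid records, and a subject removed by rule has not revoked authorization. Scheduled liver testing is the same in both arms: "Subjects in both arms will have their liver enzymes tested at enrollment and at the 3-, 6-, and 12-month research visits". Pregnancy should be rare, since the cited dataset reports "124 were male and 5 were female", or 5/129 = 3.9% women. GGT can come from clinical care, and Aim 2c promises missing-data sensitivity analyses, though without naming a method. These protect visit counts but do not restore TLFB, EQ-5D, SIP-2R or CDT. Consent pages and attachments were not available and may say more.

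A reader might also infer further contradictions, which the documents do not support. The wallet-card sentence ("In case of an emergency situation requiring opioids, subjects will be provided with a card showing that they have (or have not) received XR-NTX") concerns emergency care and is silent on participation. "Otherwise, subjects may receive any concomitant medical therapy" is a general statement on concomitant treatment. Section 13 retains subjects who are incarcerated, which is a different event from a contraindication.

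**Conclusion.** The point holds as a conflict between a stated rule and the stated analysis population, together with a gap in Section 4.4.2. It should be fixed, at the lower end of that grade.

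Three stronger conclusions would go too far:

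- No section says that research visits stop; that follows only from a literal reading.
- Unequal removal is possible because checks are more frequent in the intervention arm, but nothing shows that it will occur or in which direction.
- The intention-to-treat analysis of healthcare use is not defeated. It is largely protected if record sources are used, although the plan lists them subject to availability and does not say they continue after withdrawal.

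The likely size is modest: 0.04 to 0.08 SD in the most unequal case shown, and zero with equal removal and equal δ. All of this rests on assumed rates and differences, because the documents give none. Phase 1 effect analyses are exploratory, so bias matters mainly for phase 2, which is meant to test effects definitively.

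**What to change.** Reconcile Sections 1.6.1, 4.3.6, 4.4.1 and 4.4.2. All rules on when XR-NTX is given, stopped or resumed stay with the sponsor; only data collection is at issue here.

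- In 4.4.1 and 4.4.2, distinguish the end of study treatment from the end of follow-up. State that subjects in either arm who leave for any reason other than withdrawal of consent or authorization remain, where they agree, in the week 12, 24 and 48 research assessments.
- State that record-based and vital-status follow-up continues for them through 12 months, and that they are analysed in the arm to which they were randomized.
- In 7.2.2, report rule-based withdrawals by arm alongside the Aim 1 completion proportions.

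The cost is an IRB amendment, which needs care because Section 4.3.6 is subject-protection text, and a few more follow-up contacts. Record sources and mortality tracking are already planned, the records subject to availability.
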